- To compare the rates of side effects following SD-QIV and HD-TIV (*Safety*).
- To test for associations between disease and patient characteristics, and vaccine-induced protection for SD-QIV and HD-TIV (*Predictors of response to influenza vaccine in RA*).

3) Exploratory objectives

- To assess the performance of microneutralization (MN) and single radial hemolysis (SRH) assays compared to the HI assay in SD-QIV and HD-TIV recipients with RA (*Serologic readouts*).
- To describe the poly-functional CD4⁺ T-cell response to the SD-QIV and HD-TIV formulations for each strain (*Cellular immune responses*).
- To describe the rates of pneumonia and health care use (hospitalizations, emergency room visits, and other physician contacts) in patients receiving SD-QIV or HD-TIV (*Clinical impact*).

4. Recruitment Process

Pre-recruitment of study candidates will be done by rheumatologists working at the (A) Montreal General Hospital (MUHC), (B) Royal Victoria Hospital (MUHC), and (C) Sir Mortimer B. Davis – Jewish General Hospital prior to the start of the 2016-17 and 2017-18 influenza seasons.

5. Study Period

This study will begin as soon as the SD-QIV and HD-TIV vaccines become available in Quebec for the 2016-17 (Year 1) and 2017-18 (Year2) influenza seasons. Active enrollment each year will continue until December 30th. The duration of each subject's participation in the respective study years will be 186 days.

6. Main Criteria for Inclusion/Exclusion

Adult (>18 years old) females or males with a diagnosis of seropositive (rheumatoid factor (RF) and/or anti-CCP antibody positive) RA treated for at least 6 months with any of the following agents as mono- or combo- therapy: DMARDs (i.e. methotrexate, hydroxychloroquine, sulfasalazine), biologics (i.e. anti-TNF, abatacept, rituximab, tocilizumab) or small molecules (tofacitinib). No major changes of DMARDs or biologics should have occurred in the 30 days prior to enrollment, and no intention to switch therapy within 30 days following vaccination should be present.

Subjects must be accessible by phone or text on a consistent basis and available at day 28.

Subjects who have received vaccination against influenza in the 6 months preceding the trial vaccination or with any of the following conditions will be excluded from enrollment:

- Systemic hypersensitivity to eggs, or any of the vaccine components, or a history of a life-threatening reaction to TIV or to a vaccine containing any of the same substances.

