- Seroconversion rate (SCR): The proportion of subjects in a given treatment group with either a \geq 4-fold increase in reciprocal HI titers between d0 and d21; or a rise of undetectable HI titer (ie, < 10) pre-vaccination (d0) to an HI titer of \geq 40 at d28 post-vaccination. The lower bound of the two-sided 95% confidence interval (CI) for the percent of subjects achieving seroconversion for HI antibody should meet or exceed 40%.
- Seroprotection rate (SPR): The proportion of subjects in a given treatment group attaining a reciprocal HI titer of \geq 40 at 28 days post-vaccination (the percentage of vaccine recipients with a serum HI titer of at least 1:40 following vaccination). The lower bound of the two-sided 95% CI for the percent of subjects achieving an HI antibody titer $>$ 1:40 should meet or exceed 70%.

In addition, immunogenicity will be evaluated by seroconversion factor or the geometric mean fold rise (GMFR):

- GMFR: The geometric mean of the ratio of GMTs (d28/d0). The mean GMFR should be $>$ 2.5

Antibody Persistence (Secondary objective): HI antibody persistence will be assessed by comparing the proportions of SPR and GMTs at D186 (+3) between SD-QIV and HD-TIV. A difference of at least 20% will be considered significant.

MN and SRH data (Exploratory objectives): These functional antibody responses will be assessed during Y3 for at least 10 patients in each of the SD-QIV and HD-TIV groups to assess the performance characteristics of these assays in the RA patient population. These data will be described in the same terms as the HI results for each strain.

Cellular Immune responses (Explorative objective): Cellular responses will also be performed during Y3 using cryopreserved PBMCs from at least 60 RA patients (10 patients x 3 strata x 2 arms).

10- Clinical Data

Demographic characteristics (age, sex, ethnic background),

Comorbidities (Charlson comorbidity index + year of diagnosis)

Vaccination history (including last seasonal influenza vaccination, and last pneumococcal vaccination)

Information on RA:

- 1) Year of onset of RA symptoms (reported by patient)
- 2) Year of RA diagnosis (reported by patient/documentied in medical record)
- 3) Complete medication list (at the time of consult)
- 4) Number and type of DMARDs/biologics used (ever)
- 5) Use of steroids during the 6 months prior to consult (dose/route/frequency)
- 6) BMI

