- 7) Disease activity: Number of tender joints / number of swollen joints / acute phase reactants (CRP/ESR)/ patient global (VAS) – DAS28 score

8) Extra-articular manifestations (i.e. interstitial lung disease, subcutaneous nodules, sicca symptoms, vasculitis; + year of diagnosis)

9) Joint replacement surgeries

10) Health Assessment Questionnaire (HAQ)

11) Tobacco use and alcohol consumption

12) Hospitalizations during the last 12 months (and cause)

13) Number of times that the patient had previously received the influenza vaccine

From the laboratory results closer to D0 the following values will be obtained: hemoglobin, lymphocyte count, ESR, CRP, creatinine, RF, CCP.

TABLE 1: TIME AND EVENTS SCHEDULE

	Pre-recruitment Stratification Randomization	Visit 1	Phone call	Visit 2	Visit 3	Monthly phone calls / May 15th
	Assign patients to specific Day 0 study date					
Study day	Day -120 to -1	Day 0	Day 7	Day 28	Day 183	
Permissible visit window (days)			-1/+3	±3	±7	
Clinical Procedures						
Explain trial/ eligibility criteria		X				
Consent		X				
Collection of clinical data and RA activity		X		X	X	
BMI		X				
Medication list		X		X	X	X
Vaccine administration		X				
Immunogenicity tests						
Serologies (10 mL)		X		X	X	
Safety Assessments						
30 minutes post vaccine		X				
Interval events			X	X	X	X
Visit schedule						
Confirm visit		X		X

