NCT number: NCT02936180

**Study title: Improving Influenza Immunization Responses in Rheumatoid Arthritis: A Strategy
To Enhance Protection Against A Preventable Cause Of Death In An At Risk Population?**

Date: 20 November 2019

Statistical Analysis

This study was powered to compare the effect of the HDTIV and SDQIV by background treatment group (stratified analyses), estimating a loss to followup of 10%. Under these assumptions, 92 rheumatoid arthritis patients per strata (46 per vaccine group) were required to assess the primary outcome with a significance level of 5% and 80% power to detect a 30% increase in sero conversion rate for any one common viral strain in the HDTIV group compared with the standard-dose vaccine. This did not include adjustment for multiple testing. Differences of this magnitude have been reported for some strains in immunogenicity studies of HDTIV in older individuals.²⁸

We did a modified intention-to-treat analysis of all outcomes with all randomly assigned participants for whom serostatus was available. The analysis included individuals who did not complete all specified followup visits. We did not do imputations at day 28 as only five patients (<2%) of 279 had missing information for serostatus.

We performed logistic regression and report crude odds ratios (ORs) with 95% CIs to compare the immunogenicity of HDTIV versus the SDQIV for each inactivated influenza vaccine strain. We also calculated ORs (95% CIs) adjusted for age, comorbidities known to reduce immune responses to inactivated influenza vaccines in the general population,⁹ and rheumatoid arthritis disease duration (which predicts the risk of comorbidities).

In a posthoc analysis we performed logistic regression to assess the effect of methotrexate (measured by OR [95% CI]) on responses to HDTIV versus SDQIV. We compared patients on methotrexate (alone or combined with other conventional synthetic DMARDs) versus those on single or combinations of nonmethotrexate conventional synthetic DMARDs, and patients on methotrexate (alone or in combination with other conventional synthetic DMARDs) versus those on biological DMARDs (except rituximab), alone or combined with nonmethotrexate conventional synthetic DMARDs.

A second posthoc analysis using the same method was done to assess the immunogenicity of HDTIV in patients on conventional synthetic DMARDs or targeted synthetic DMARDs versus those on biological DMARDs (excluding rituximab).

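### The adjusted logistic model leaves out Day 0 HI titre, treatment stratum, season and prior influenza vaccination, giving up modest power and protection against chance imbalance

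*SAP*

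**What the plan says.** The SAP (Statistical Analysis, third paragraph) gives two estimates per strain. The first is unadjusted: "We performed logistic regression and report crude odds ratios (ORs) with 95% CIs". The second is adjusted: "We also calculated ORs (95% CIs) adjusted for age, comorbidities known to reduce immune responses", together with "rheumatoid arthritis disease duration (which predicts the risk of comorbidities". No other covariate is listed. The SAP does not say whether these models are fitted within strata, in the pooled data, or both.

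Four other variables are available:

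- **Day 0 HI titre.** Serology is drawn at Visit 1 (Protocol section 7). Seroconversion is defined in section 9 as a change from that value.
- **Treatment stratum.** Randomisation is stratified by RA treatment into three groups (sections 1 and 7).
- **Season.** Recruitment covers 2016-17 and 2017-18, and nobody may take part in both (sections 1 and 6).
- **Influenza vaccination history.** Section 10 asks for it twice: "Vaccination history (including last seasonal influenza vaccination, and last pneumococcal vaccination" and "Number of times that the patient had previously received the influenza vaccine". Section 6 excludes "Subjects who have received vaccination against influenza in the 6 months preceding the trial vaccination", so the variable describes earlier seasons.

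A secondary objective (section 3) is "To test for associations between disease and patient characteristics, and vaccine-induced protection for SD-QIV and HD-TIV". It does not name vaccination history.

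**The concern.** The SAP's own reason for choosing covariates is their link to vaccine response. Comorbidities are included because they are known to weaken it, and disease duration because it predicts comorbidities, which is one step further removed. By that reasoning the starting antibody level, which is part of the endpoint, has a stronger claim, and previous vaccination against the same disease is at least as close. The stratum was judged important enough to control in randomisation but is not among the listed covariates. The season is also known for everyone.

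At stake are power and robustness. The trial was sized by stratum, and in groups that small a prognostic variable can differ between arms by chance. The listed covariates would not correct for this.

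**Working it through.** **1. The plan's sample size.** SAP inputs: 5% significance, 80% power, a 30% increase in seroconversion, 10% loss, 46 per vaccine group per stratum. The control rate and sidedness are not stated. I assume 25% versus 55% (30 percentage points), two-sided.

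n = [1.96·√(2×0.40×0.60) + 0.8416·√(0.25×0.75 + 0.55×0.45)]² / 0.30² = 40.7, so 41 per arm. Then 41/0.9 = 45.6, so 46. The plan's figure is reproduced, with about 41 evaluable per arm in a stratum. The pooled analysis has 279 − 5 = 274 patients.

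**2. Chance imbalance.** For a binary covariate with prevalence p, the between-arm difference has SD √(2p(1−p)/n). Prevalence of prior vaccination is not given, so 50% to 85% is assumed.

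| | p = 50% | p = 70% | p = 85% |
|---|---|---|---|
| 46 per arm | 10.4 points | 9.6 | 7.4 |
| 137 per arm | 6.0 | 5.5 | 4.3 |

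At 41 per arm and p = 60%, it is √(2×0.6×0.4/41) = 10.8 points. If prior vaccination lowered seroconversion by 25 points (assumed), a one-SD imbalance would move the crude difference by 0.25 × 10.8 = 2.7 points. The standard error of that difference is √(0.25×0.75/41 + 0.55×0.45/41) = 10.3 points, so the share of variance is (2.7/10.3)² = 7%.

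**3. Effect of adding one covariate.** Logistic models with and without prior vaccination were simulated (1,500 trials per scenario; control rate 25%; prevalence 50%, 70% or 85%). The treatment OR was 2.0 at N = 274 and 3.67 at N = 92. The covariate OR was varied.

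| Covariate OR | SE of log OR, N = 274 | Power change, N = 274 | SE, N = 92 | Power change, N = 92 |
|---|---|---|---|---|
| 1 | about 0.265 to 0.266 | within 0.5 point | 0.461 to 0.467–0.468 | within 0.2 point |
| 0.5 | 0.265 to 0.268–0.270 | +1 to +2 | 0.46 to 0.474–0.476 | +0.5 to +1.5 |
| 0.33 | 0.265–0.266 to 0.273–0.277 | +2 to +3 | 0.46 to 0.482–0.489 | +1 to +3 |
| 0.2 | 0.266 to 0.281–0.288 | +4 to +5 | 0.46 to 0.496–0.517 | +3 to +7 |

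The standard error never falls. Power rises because the conditional OR lies further from 1. Across assumed effects for the available variables, the change is roughly 0 to +9 points when they are prognostic and −2 to 0 when they are not.

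**4. Does the titre make vaccination history redundant?** In simulations where prior vaccination also reduced the rise directly (by about 25 points), adding it changed power from 65% to 70%, 58% to 64% and 73% to 77%. Day 0 titre alone added 0 to 2 points. Where there was no direct effect, prior vaccination added nothing. The documents do not say which case applies.

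**5. How many covariates the data can carry.** In one stratum at 25% versus 55%, there are about 41×0.25 + 41×0.55 = 33 seroconverters. Arm, age, one comorbidity term, duration, titre, prior vaccination and season make 7 parameters: 33/7 = 4.7 events each, which is too few. Arm, titre and prior vaccination make 3: 33/3 = 11. In the pooled data, 137×0.25 + 137×0.55 = 110 seroconverters over 9 parameters (those 7 plus two stratum terms) gives 12.

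**The case against.** The strongest reply is that nothing is broken. Allocation is random and stratified by treatment, the crude OR is reported, and its confidence interval already allows for chance imbalance. A shift of 2.7 points against a standard error of 10.3 is small. The SAP gives a reason for its covariates, and a similar argument could be made for many items in Protocol section 10. No passage says that prior vaccination affects the HI response, so the gain rests on assumed effects. The SAP is dated 20 November 2019 and written in the past tense, so choosing covariates now is post hoc. Adding four variables within a stratum would also overload the model.

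Most of this stands, and it limits both the size of the point and the remedy. It does not remove the omission. Day 0 titre and stratum are not arbitrary picks from a long list: one is part of the endpoint definition and the other is a design factor. The predictors-of-response objective adds little, because it is a separate analysis and does not require these variables in the treatment comparison.

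A reader might infer that the plan loses precision, with wider intervals than necessary. That does not follow for a logistic model: the standard error of the log OR stays level or rises when a prognostic covariate is added.

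**Conclusion.** The point holds as a minor one. The adjusted model omits four available variables with a good claim to inclusion, and the SAP does not say why. The cost is roughly 0 to 9 points of power if they are prognostic, towards the low end for weak or moderate effects, plus unadjusted chance imbalance with an SD of about 7 to 11 points per stratum for prior vaccination. If the variables are unrelated to response, including them would change power by about −2 to 0 points. The range rests on assumed prevalences, covariate effects and a 25% control rate, none of which the documents give.

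Two stronger readings are not supported. One is that the omission biases the vaccine comparison: randomisation prevents that, and the crude OR remains valid for what it estimates. The other is that the improvement is free: vaccination history may be misremembered or missing, and the adjusted OR becomes more conditional, so it does not estimate the same quantity as the crude one.

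**What to change.** In the pooled analysis (about 274 patients), add to the adjusted logistic model for each strain: log2 Day 0 HI titre for that strain, with a stated value for titres below the detection limit; treatment stratum; season; and last-season influenza vaccination (yes/no). Report it beside the crude OR and label it post hoc or sensitivity. State how missing vaccination history is handled, and do not read a gap between the crude and adjusted ORs as evidence of confounding.

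Within a single stratum (about 41 per arm), limit the covariates to Day 0 titre and prior vaccination.

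If no new model is fitted, tabulate Day 0 titre and prior vaccination by arm and stratum, and give the reason for leaving them out.

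The cost is one further model per strain on scheduled data, with four added variables (five parameters, since stratum needs two). The downsides are recall error or missing history, a more conditional OR, and up to about 2 points of power if the variables prove unrelated.
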